Cognitive training. The type of CT that produces the best cognitive function outcomes is unknown since many studies have enrolled predominately healthy, well-educated white individuals with no CI.⁶⁴⁻⁶⁶ Research in adults with CI are inconclusive and have considerable limitations; few randomized trials are available.^{64-66,88} Several recent studies suggest that computer-based plasticity interventions may be advantageous, e.g. in memory training.⁸⁹⁻⁹¹ Plasticity-based training interventions hinge on the understanding that targeted, repeated cognitive exercises can rebuild and re-organize function through neuronal generation, dendritic sprouting, and axonal sprouting. The only study to date to incorporate plasticity-based cognitive training in HF found that it significantly increased list learning, delayed recall memory, psychomotor speed, and performance of IADLs; participant adherence and satisfaction were high.¹⁶ In another study of community dwelling older adults without CI, improvement in memory and attention was significantly greater in the group that received the plasticity-based cognitive training intervention than in those receiving a program of general cognitive stimulation.

Combined exercise and CT. Evidence of exercise improving cognitive function is **robust**; and similar changes on cognition are noted with plasticity-based CT; the effects of these two approaches are different yet synergistic, and suggest the effect on cognitive functioning may be more pronounced when the two are used in combination versus alone; this provides a strong rationale for the proposed intervention.⁵²⁻⁶⁶ This feasibility study will evaluate the acceptability of the intervention(s), adherence to the intervention protocols, the scope of

recruitment efforts to identify acceptable cases, potential dose responses gleaned from differing amounts of intervention compliance, and estimates of effect sizes to optimize a subsequent, large-scale efficacy trial.

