Group 3: Ex only group (UC + aerobic exercise). The same exercise protocol will be used as above without the computer training.

Exercise adherence. To be 100% adherent for exercise sessions, participants in both groups 2 and 3 must document walking weekly at the prescribed intensity/duration on the exercise log. Participants will record on a calendar provided: maximum HR achieved; rate of perceived exertion (RPE) during walk; and number of steps walked during the walking sessions. Polar HR monitors and pedometers (described in instruments) will be used to objectively document exercise intensity (i.e., maximum HR and RPE achieved), duration, walking adherence and progression. The Polar HR monitor and pedometer data will be downloaded during each home visit during the first 2 weeks to track exercise duration and steps walked. At T2, data collected from the HR monitors and pedometers will also be downloaded to document exercise adherence. A total summary adherence score will be calculated by summing and dividing weekly adherence scores by total number of weeks walked.

CT adherence. The total number of minutes for the full Brain Fitness program is approximately 2400 minutes over 8 weeks. Patients will be considered adherent if they meet or exceed 80% of the required minutes for the intervention. Total number of minutes can be accessed from the program to monitor adherence.

VARIABLES, DEFINITIONS AND MEASURES. Variables, operational definitions and methods are described below and in Table 3. Questionnaires will be administered at the time of the visit by a trained research assistant blinded to group allocation. Core services and Center activities will greatly enhance the success of this study. Through training and monitoring in administration and scoring of the core test battery, regular consultation with the BMC to monitor implementation issues, systematic data management and analysis, and support in using these findings to prepare an RO1 application, this study will achieve its aims and further the goals of this Center.

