Exercise Adherence	Polar HR (intensity, duration and frequency), walk calendars, pedometer, nurse telephonic log	10 minutes	3 and 6 months
CT adherence	Brain Fitness program, nurse telephonic log	NA	

Physical Function will be assessed using the **modified Balke maximal treadmill test** ¹⁰⁶⁻¹⁰⁷ to determine peak oxygen consumption (peak VO_2), maximum HR for exercise prescription and to screen for cardiac contraindications to exercise according to the (AHA/ACC) guidelines. ¹⁰² **Physiological status.** The serum biomarker **BDNF** will be collected in the CIN by a research nurse or phlebotomist, the assays will be stored at -80 degrees until processed by the ACTSI biocore lab using the manufacturer's ELISA guidelines.

QOL. The **Kansas City Cardiomyopathy Questionnaire (KCCQ)** ¹¹⁰ is a reliable and well validated 23-item, disease specific questionnaire that quantifies physical function, symptoms, social function, and HRQOL in HF. ¹¹¹⁻¹¹²

Adherence. Step counts will be indirectly assessed using the Omron HJ-7201ITC pedometer to count daily steps. ¹¹³⁻¹¹⁷ The 15 point (6-20) **Borg Rate of Perceived Exertion (RPE) Scale** ¹¹⁸ will be used to measure participants' subjective perception of effort. **Target heart range (THR)** ¹⁰⁷ using the HR reserve method will be used to monitor the intensity and training response to walking. Polar Beat ® Watch (FT4) ¹¹⁹ will be used to monitor intensity and duration of walking. ¹²⁰⁻¹²¹ Actual adherence to intervention protocols and study attrition rates will be included in an intent-to-treat analysis (CT & Ex).

Acceptability. During post-baseline visits and phone contacts, participant's opinions about the intervention, e.g. perceived usefulness, ease of use, barriers to adherence, perceived improvements in health, cognition, mood, quality of life will be collected. The PI will use content analytic techniques to assess acceptability and to identify themes suggesting possible revisions or alterations in the interventions that might improve acceptability.

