Procedures Recruitment, Screening and Enrollment of participants will occur through physician and other health care provider referrals and patient self-referral. These methods have proved successful in our prior work. The recruitment nurse will arrange a time for laboratory, and treadmill tests at the CIN. Baseline (T1) measures will be taken in the CIN by a trained data collector blinded to group assignment. All participants will be given the same measures, in the same sequence at each time point. Questionnaire completion should take 30 minutes or less, the neuropsychological testing is anticipated to take 75 minutes. Laboratory samples will be taken prior to the treadmill test. The BDNF samples will be stored at -80 in the CIN until processed. After the laboratory work is completed, the modified Balke treadmill test will be conducted by an exercise physiologist; emergency equipment, doctors and nurses are available. After BL, participants will be randomized to study groups by computerized sheet prepared by the study statistician. At 3 and 6 months we will follow the same procedures used at Evaluation 1. After Evaluation 3, participants will be discharged from the study, and all participants provided with study results. A \$50 honorarium will be provided at each measurement time point, to total \$150/patient for completing the study. Intervention process measures (evaluation, attendance) will be tracked and evaluated to maintain internal validity. Protocol adherence will be calculated for both groups.

Data Management and Analysis. The Biobehavioral and Methods Core (BMC) will coordinate the collection, integration, and analysis of biological and psychosocial data for this study. Data will be analyzed using both descriptive and inferential test statistics. We will build multivariable statistical models to examine the relationship between an Ex/CT intervention to exercise alone and attention control (AC) on cognitive functioning (P-30 Neuropsychological Battery), cerebral oxygenation (NIRS, 3 months only), physiological status (BDNF), physical function (peak VO_2) and QOL (KCCQ) in HF at BL, 3 and 6 months controlling for but not limited to age, gender, SES, depression, social support, NYHA class, medications and comorbidities.

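### The exercise adherence score is divided by weeks walked, so within the 12-week prescription unwalked weeks drop out and early stopping does not lower the score

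*Combined protocol and SAP*

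**What the plan says.** Section C (Approach), paragraph on exercise adherence, gives the condition for 100% adherence: "participants in both groups 2 and 3 must document walking weekly at the prescribed intensity/duration on the exercise log". The same paragraph ends with the scoring rule: "A total summary adherence score will be calculated by summing and dividing weekly adherence scores by total number of weeks walked". It gives no formula for a weekly score. It does not say how an unwalked week, or a week after withdrawal, is scored.

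The next paragraph treats cognitive training differently. The requirement is fixed: "The total number of minutes for the full Brain Fitness program is approximately 2400 minutes over 8 weeks". So is the test: "Patients will be considered adherent if they meet or exceed 80% of the required minutes for the intervention".

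Table 2 (exercise prescription for Groups 2 and 3) runs from week 1 to week 12, with three sessions in every week. Table 3 lists the sources for exercise adherence as "Polar HR (intensity, duration and frequency), walk calendars, pedometer, nurse telephonic log", evaluated at 3 and 6 months.

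Section A, under combined exercise and CT, says the study will evaluate "adherence to the intervention protocols" and "potential dose responses gleaned from differing amounts of intervention compliance".

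**The concern.** A participant who stops early is judged only on the weeks before stopping, and a participant who never starts has a score of 0/0 and falls out of any average. The summary can therefore be high although little of the prescribed programme was done. This sits badly with the condition for 100% in the same paragraph, which asks for walking every week. Within the EX/CT arm, stopping both components early lowers the training figure but need not lower the exercise figure, so the two cannot be compared.

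Aim 1 is feasibility, and adherence is one of the outputs meant to inform the later efficacy trial. This is the only summary exercise adherence score that the documents define. If it were also used as the measure of dose, participants could be ranked in the wrong order of exercise done.

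**Working it through.** The plan gives no numerical value for the score, so there is no figure to reproduce. The check is algebra on the rule.

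**Inputs**
- Table 2: 12 weeks, 3 sessions per week; 30 minutes in weeks 1-2 and 45 minutes in weeks 3-12.
- Denominator: weeks walked, W (exercise adherence paragraph).
- Cognitive training: about 2,400 minutes, 80% criterion (CT adherence paragraph).
- Arm size: 20 (Specific Aims) or 25 (Design).
- Assumption: an unwalked week contributes 0 to the sum. No other property of the weekly score is needed for step 2.

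**1. Prescribed dose.** Sessions: 12 × 3 = 36. Minutes: 2 × 3 × 30 + 10 × 3 × 45 = 180 + 1,350 = 1,530.

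**2. Ratio of the two scores.** Let S be the sum of weekly scores over weeks 1-12, with 1 ≤ W ≤ 12. The score as written is S/W and the 12-week score is S/12. For S above 0 their ratio is 12/W, which is at least 1.

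| Weeks walked (W) | 12/W | 12-week score if every walked week is full | Score as written |
|---|---|---|---|
| 12 | 1.0 | 100% | 100% |
| 10 | 1.2 | 83.3% | 100% |
| 8 | 1.5 | 66.7% | 100% |
| 6 | 2.0 | 50.0% | 100% |
| 4 | 3.0 | 33.3% | 100% |

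As a check, all 455 combinations of twelve weekly scores from 0, 1/3, 2/3 and 1 were enumerated (assumed scoring: sessions done out of 3). In none was the written score below the 12-week score. In 91 they were equal, exactly those with all 12 weeks walked. In 363 the written score was higher. One, with no week walked, was undefined.

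**3. Ranking by dose.** Participant A walks fully for 4 weeks and stops: 12 of 36 sessions (33.3%) and 180 + 270 = 450 of 1,530 minutes (29.4%). The score as written is 100%. Participant B walks all 12 weeks at 80%: 0.8 × 1,530 = 1,224 minutes, and the score is 80%. B did 1,224/450 = 2.7 times the minutes of A but ranks below A.

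**4. Contrast with cognitive training.** The criterion is 0.8 × 2,400 = 1,920 minutes, whatever the number of weeks in which training took place.

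**5. Dependence on the window.** The inequality in step 2 needs scoring to end at week 12. Twelve full weeks plus a week 13 at 1/3 gives 12.33/13 = 94.9%, below the 12-week score of 100%.

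**6. Arm level.** A participant who stops after week k, with mean score b in the weeks walked, raises the mean of an arm of n by b × (12 − k)/12 ÷ n. The documents give neither k nor b. For k = 4 (assumed):
- b = 80% (assumed): 53.3/20 = 2.7 points, or 53.3/25 = 2.1.
- b = 40% (assumed): 26.7/20 = 1.3 points, or 26.7/25 = 1.1.

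**The case against.** The strongest reply is that weeks walked was meant as the length of the walking programme. The denominator would then be 12 and the bias zero, and the weekly documentation requirement favours that intention. But no section says so, and the literal words point the other way. The text needs a clarifying line on either reading.

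Second, early stopping is not hidden. The Adherence paragraph of Section C brings both adherence and attrition into an intention-to-treat analysis, Section E promises actual retention rates as feasibility results, and Procedures adds: "Intervention process measures (evaluation, attendance) will be tracked and evaluated to maintain internal validity". This stands in part: a reader of the results would see that people left. It does not correct the score, and a participant who attends every visit but has stopped walking does not count as attrition.

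Third, nothing decisive depends on the score. The documents attach no exercise adherence threshold, progression criterion or model to it, the study is declared exploratory, and dose could be measured from monitor, pedometer and calendar data instead. This also stands, and it limits the consequence.

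A reader might infer that the score can never fall below the 12-week score under any circumstances. The documents do not support that. Monitors are downloaded at T2, in weeks 13-14, and again at 6 months, and the scoring rule does not itself stop at week 12. A 12-week window is the natural reading, because the rule follows the T2 download and Table 2 ends at week 12, but it remains a condition.

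**Conclusion.** The point holds, with conditions. On the plain reading, and with scoring confined to weeks 1-12, the rule overstates adherence by the factor 12/W for anyone with a positive score who misses a whole week, gives no score to a participant who never walks, and can reverse the order of participants by dose. It contradicts the standard for 100% in its own paragraph, and no other section repairs it.

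The participant-level result rests on Table 2 and on counting an unwalked week as 0. The arm-level size is unknown: the 1.1 to 2.7 points per early stopper are illustrations on assumed inputs, and the gap is zero if everyone walks in all 12 weeks. The expected 85% retention cannot stand in for a rate of stopping walking, since it refers to staying in the study.

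A reader might also infer that the trial's feasibility conclusion or its dose-response work will be wrong. That goes too far: Section A does not name this score as the dose measure, and no decision rule uses it. What is established is that a named feasibility output has a denominator that can misreport it. This should be corrected before adherence is summarised.

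**What to change.** For every randomised participant in the two exercise arms, define the score as qualifying sessions out of the 36 prescribed in weeks 1-12. Equivalently, take each week's proportion of its 3 sessions, sum over weeks and divide by 12. Score unwalked weeks and weeks after withdrawal as 0. This also supplies the missing formula for the weekly score. State what makes a session qualify, since Section E lets some participants be guided by perceived exertion or held at their current level.

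Report W and the walked-weeks mean beside the score. The 12-week score equals the walked-weeks mean times W/12, so persistence and adherence while walking stay separable and the quantity now defined is not lost. Keep data after week 12 out of this score. Flag sessions withheld under the protocol's own instructions where the telephone log gives the reason.

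The rule uses logs, downloads and call records already planned and can be applied at analysis. The reported adherence figure will be lower. After the downloads of the first 2 weeks the next is at T2, so for participants who withdraw before T2 the later weeks rest largely on the telephone log. The documents do not list the reason for a missed session as a recorded item, so the flag for withheld sessions may be incomplete.

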Sociodemographic and clinical variables will be obtained from self-report and medical records. The Charlson Comorbidity Index (CMI)¹⁰⁸ will quantify the cumulative risk of death. **Mini Mental Status Examination**¹⁰² will be used to screen for study inclusion for mild to moderate cognitive impairment (score of 20 for 8-9 yrs of schooling; 22 for 10-12 yrs of schooling; 23 for >12 yrs)¹⁰² and has excellent specificity at this cut-off point.⁵

The **Beck Depression Inventory-II** (BDI-II)¹⁰⁹ has been widely used in the HF population. Scores will be used as an effect modifier and explored as a potential outcome variable. **Cognitive Function.** We will use the

Center’s core neuropsychological testing battery of well-established and validated instruments that are described in the Biobehavior and Methods Core (BMC) portion of this application. The BMC will provide training on test administration and scoring and will aid in data management and interpretation. Cerebral tissue oxygenation will be assessed in the CIN by a cerebral oximeter sensor (Casmed, Blanton, CT) using near infrared spectrography (NIRS). NIRS is widely used and validated in a variety of fields to assess cerebral tissue oxygenation.^{86,101}

Table 3. Variables, measures, instruments and time of evaluation

Variable	Measure/Instrument	# of items/time	Time of Evaluation
Antecedents Participant Demographics & Clinical information: Co-morbidity, Cardiac Fx, Meds	Age, gender, education, marital status, Charlson comorbidity Index (CMI) LVEF, NYHA class, length of time with HF & etiology, Medications	Chart review & questionnaire Questionnaire	Baseline (BL)
Mild-moderate cognitive impairment	MMSE	30 item/10 minutes	BL only
Depressive symptoms	BDI-II	21 item/15 minutes	BL only
Cognitive function	Repeatable Battery for the Assessment of Neuropsychological Status (RBANS) Controlled Oral Word Association Test Color Trails 1 & 2 WAIS-III Digit Span/Letter Number Sequence Stroop Test Ruff 2 & 7 Test Rey Auditory Verbal Learning Test	30 minutes 5 minutes 10 minutes 10 minutes 5 minutes 5 minutes 10 minutes	BL, 3 and 6 months

Physical function	Peak oxygen consumption (Modified Balke)	20 minutes	BL & 3 mos
Physiological status	BDNF	NA	BL & 3 mos
Cerebral oxygenation	Near infrared spectography,	30 minutes	BL & 3 mos
Quality of Life	KCCQ	23 items /15 minutes	BL, 3 and 6 months

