Sources of research material will include responses to questionnaires **obtained at baseline, 3 and 6 months**; data will also be obtained at these time points in the form of laboratory serum samples, treadmill and neuropsychological tests. Polar HR monitors and pedometers will be downloaded weekly during the first 2 weeks to obtain data on adherence to prescribed exercise intensity and duration and at 3 and 6 months. Calendar walking logs will be used to obtain data on exercise adherence for the exercise sessions. The participant's medical history, medication history and sociodemographic information will be obtained from the medical record. It is expected to take approximately 30 minutes for the participants to complete the questionnaires at each time point. The neuropsychological tests are anticipated to take approximately 75 minutes. Each participant is anticipated to spend approximately 3 hours at each time point for data collection purposes. A trained research assistant blinded to study group assignment will administer the questionnaires at the ACTSI at each visit in the same sequence for each time point. All data will be obtained specifically for research purposes and in the same order and sequence at each testing period. Participants in each group will have 2 home visits during the first 2 weeks of the study followed by weekly telephone contact from 3-12 weeks and bi-monthly telephone contacts from 15-24 weeks. Participants randomized to the exercise/CT and exercise only group will have one supervised walking sessions to establish safety, explain use of pedometers, HR monitors and calendars. Participants randomized to the exercise/CT group will have 2 home visits during the first 2 weeks to explain and review how to use the Brain Fitness program (in combination with one supervised walk session). The AC group will also have 2 home visits in the first 2 weeks to demonstrate stretching and flexibility exercises and to review HF educational materials. At the end of 12 weeks, the participants will undergo T2 measures at the ACTSI at weeks 13 and 14 (3 months evaluation). At the end of the 6 months, T3 measures will be scheduled at weeks 25 and 26. Printed education materials will be standardized across all groups. The total participation time over 12 weeks is anticipated to be 40 hours for the exercise only and AC groups, including testing time. The total estimated time for the exercise and CT group is anticipated to be approximately 80 hours including testing time.

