Potential risks related to questionnaire completion include the possibility of distress after the instrument administration or teaching session. Based on the preliminary work and patient responses to these types of questionnaires and interventions, we anticipate this risk to be minimal. The intervention should not increase distress over usual care. We also observed no increase in patient depressive symptom scores over time in other studies suggesting that the intervention did not introduce greater distress. However, if participants do indicate significant symptoms of depression by their responses on the BDI-II, mental health referral information will be provided and they will be asked if they would like a research team member to assist them in setting up a referral. If at any time a participant indicates serious depressive symptoms or an intent to hurt him or herself, a family member will be informed (as agreed in the Informed Consent form) and/or their primary care provider (or cardiologist) alerted (again as agreed to in the Informed Consent). Other risks that occur are increased burden of participating in the intervention or attention control follow up calls and clinic visits. The blood sample will be collected by a research nurse or laboratory assistant in the ACTSI at each time point. The needles and syringes will be disposed in appropriate biohazard containers. The BDNF sample will be labeled by participant identification number, time point and stored in the ACTSI at -80 degrees until analyzed using the recommended ELISA procedures by the manufacturer. All laboratory specimens will be run twice to ensure reliability of blood tests. Slight bruising at the site of the venipuncture is possible. For participants on anticoagulant therapy, additional pressure to site will be applied.

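### The documents contradict themselves on when the BDI-II is given; if Table 3 is followed, depression cannot be analysed as the exploratory outcome that the text names

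*Combined protocol and SAP*

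**What the plan says.** The combined protocol and SAP addresses the BDI-II schedule in several places.

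- **Variables, Definitions and Measures**, on the BDI-II: "Scores will be used as an effect modifier and explored as a potential outcome variable".
- **Table 3**, depressive symptoms row: "BDI-II 21 item/15 minutes BL only". The quality-of-life row (KCCQ), by contrast, reads "23 items /15 minutes BL, 3 and 6 months".
- **Procedures**: "All participants will be given the same measures, in the same sequence at each time point", and later "At 3 and 6 months we will follow the same procedures used at Evaluation 1". The same section places randomisation after the baseline assessment.
- **Human Subjects Research**, sources of research material: questionnaire responses are collected at baseline, 3 and 6 months, and "It is expected to take approximately 30 minutes for the participants to complete the questionnaires at each time point".
- **Data Management and Analysis**: depression is in the list of control variables. It is not among the modelled outcomes, which are cognition, cerebral oxygenation, BDNF, peak VO2 and KCCQ.
- **Potential Risks**, questionnaire completion: a mental health referral offer applies "if participants do indicate significant symptoms of depression by their responses on the BDI-II". No time point is given.

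**The concern.** An outcome of a randomised intervention must be measured after randomisation. Table 3 is the only schedule that goes instrument by instrument, and it gives the BDI-II no follow-up time. Staff who work from Table 3 would collect no follow-up score; staff who work from the Procedures text would collect two. The plan does not say which governs.

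What is at stake is a secondary piece of information, lost completely if Table 3 is followed. The protocol describes depression as an independent predictor of worse cognitive impairment and cites the team's earlier trial in which exercise plus cognitive behavioural therapy reduced depression. The benefits text expects the control arm may improve in psychological functioning, though for a shorter time than the intervention arms. The BDI-II is the only dedicated measure of psychological symptoms in Table 3, so with baseline scores alone that expectation could not be checked with it. A feasibility study meant to inform a larger trial would also give no estimate of change in mood by arm.

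**Working it through.** **1. The texts side by side**

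| Place | What it implies for the BDI-II |
|---|---|
| Measures text | Effect modifier (baseline is enough) and potential outcome (needs follow-up) |
| Table 3 | Baseline only |
| Procedures | Same measures at every time point, BDI-II not named |
| Human Subjects Research | Questionnaires at baseline, 3 and 6 months, BDI-II not named |
| Data Management and Analysis | Covariate; not a modelled outcome |

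The general statements do not settle the matter. Read literally, they would also repeat the MMSE, which Table 3 gives at baseline only, and would add peak VO2, BDNF and cerebral oxygenation at 6 months, where Table 3 stops at 3 months. The analysis section limits cerebral oxygenation to 3 months, which agrees with Table 3 and not with the general statements.

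**2. Does the stated questionnaire time show which schedule was meant?**

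Inputs: Table 3 instrument times; about 30 minutes of questionnaires per visit (Human Subjects Research), with 30 minutes as an upper limit in Procedures; 75 minutes of neuropsychological testing (both sections).

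- Check that Table 3 times reproduce a stated total: 30 + 5 + 10 + 10 + 5 + 5 + 10 = 75 minutes. This matches.
- BDI-II + KCCQ: 15 + 15 = 30 minutes. This matches the stated questionnaire time.
- KCCQ alone: 15 minutes.
- With the 10-minute exercise-adherence row at 3 and 6 months, if participants complete it: 15 + 10 = 25 minutes without the BDI-II, and 15 + 15 + 10 = 40 minutes with it.
- Baseline, if the MMSE counts as a questionnaire: 10 + 15 + 15 = 40 minutes, before the demographic questionnaire, for which no time is given.

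The 15 + 15 match suggests repetition but does not prove it. The stated time is approximate in one place and a ceiling in the other, and its contents are not listed.

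**3. Participants with a computable BDI-II change**

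Inputs: 60 participants (Specific Aims, analysis section) or 75 (inclusion criteria); expected retention 85% (Human Subjects Research). Assumption: every retained participant completes the BDI-II.

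- Table 3 followed: 0 of 2 follow-up scores per participant, so 0 change scores.
- BDI-II repeated: 0.85 × 60 = 51, or 0.85 × 75 = 63.75, about 64.

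**The case against.** The strongest reply is that this is a small wording slip. Depression is absent from Aims 1 to 3, from the outcomes of interest in the Design paragraph and from the modelled outcomes. The measures text speaks only of exploring it as a potential outcome. No power statement or planned model depends on it. The BDI-II is also described as part of screening, which fits a baseline-only schedule. All of this stands, and it limits the weight of the point. It does not remove the contradiction, which decides whether two rounds of data are collected.

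Four stronger readings are tempting, and the documents do not support them:

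- **That no change in depression can be computed for anyone.** This holds only if Table 3 governs, and the general statements in Procedures and Human Subjects Research point to repetition.
- **That 30 minutes of questionnaires fits only if the BDI-II is repeated.** The arithmetic above shows that the match is suggestive at most.
- **That depression cannot lead to referral after baseline.** Under Table 3 the BDI-II score would be unavailable, but the Potential Risks text also covers serious symptoms or intent to self-harm indicated at any time. Calls continue weekly in weeks 3 to 12 and bi-monthly in weeks 15 to 24, and opinions on perceived mood improvement are gathered at post-baseline contacts.
- **That an arm difference in mood would confound the cognitive comparison.** Mood change after randomisation is a possible mediator. It does not bias the randomised comparison, and depression is already a planned covariate.

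**Conclusion.** The point holds as an unresolved contradiction between the measures text, Table 3 and the general statements on repeat assessment. On Table 3, follow-up BDI-II scores number 0 in every arm, the exploratory depression outcome cannot be analysed, and the baseline score is usable only as a modifier or covariate. On the general statements, roughly 51 (of 60) or 64 (of 75) participants would contribute a change score, assuming 85% retention and complete BDI-II forms among those retained.

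The impact is low. The aims and the planned models for cognition, oxygenation, BDNF, peak VO2 and KCCQ are unaffected. It is still worth correcting because the correction is cheap and a missed follow-up score cannot be obtained later.

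**What to change.** Choose one of two routes.

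1. **Keep depression as an exploratory outcome.** Set the BDI-II row of Table 3 to baseline, 3 and 6 months. Add depression as an exploratory outcome in Data Management and Analysis. State there that only the baseline BDI-II score is used as covariate or effect modifier, so that a post-randomisation score is not adjusted for. Cost: one table cell, a sentence or two of analysis text, and about 15 minutes at each of two visits already planned (2 × 15 = 30 minutes per participant). This is roughly consistent with the stated questionnaire time.
2. **Keep the BDI-II as a baseline measure.** Delete the clause that calls it a potential outcome and leave Table 3 as it is. Cost: one clause. If follow-up visits have already passed without the BDI-II, this is the only route left for those participants.

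Under either route, make the general statements in Procedures and Human Subjects Research refer to Table 3 for which instruments apply at which visit. Also reconcile the reference to BDI-II responses in Potential Risks with the schedule that is kept. The content of the referral procedure is for the investigators to decide.
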